7.4 Missing Data and Data Imputation Rules

All attempts will be made by the Data Management team to ensure completeness of data. Generally, missing data will not be imputed, and will be presented as collected in the study database.

In cases where adverse event (AE) or medication dates are missing, the imputation methods described in Appendix 1 will be used to determine flags for treatment-emergent events, and concomitant medications.

Other missing data methods will be proposed within the respective analysis section, as needed.

7.5 Multiple Assessments and Visit Windows

Nominal visits (e.g. those identified by the study CRF) will be the basis of summarization and statistical analysis; no visit date windowing will be conducted. Unscheduled data may be included in summaries of specific abnormalities any time post-baseline and in subject data listings.

8 STUDY SUBJECT DATA

8.1 Subject Enrollment and Disposition

Subject disposition will be summarized using the ITT set. Summaries will include the number and percent of subjects: screened, enrolled, in each analysis population, completing the study, and discontinuing study prematurely, including a description of the reason for early withdrawal. Reasons for withdrawal will include the following:

- Adverse Event
- Lost to follow-up
- Subject withdrew consent
- Protocol violation/non-compliance
- Investigator decision
- Study terminated by sponsor
- Pregnancy
- Study burden
- Tested positive for COVID-19
- Fear of contracting COVID-19
- Other

Data will be presented by disease criteria and sequence.

Screen failures, analysis populations, and final subject disposition status will be listed. Visit dates and reasons for visits not done will also be listed.

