8.5.1. Subject Disposition

Subject disposition will be summarized by LC integrity as determined by baseline disease characteristics, treatment, treatment sequence and overall using the ITT. Summaries will include the number and percent of subjects: in each analysis population, entering the treatment period, completing each period, completing the study, and discontinuing study prematurely, including a description of the reason for early withdrawal. All data will be listed.

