8.7. Analysis of Primary Endpoint

Primary endpoint data will be summarized by treatment using the Safety Set. Selected summaries may be repeated in the PPS. All data will be listed.

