3 STUDY OBJECTIVES AND ENDPOINTS

Objectives	Endpoints
Primary The primary objective of this study is to evaluate the safety and tolerability of CST-2032 when combined with CST-107.	The primary endpoint is safety and tolerability of CST-2032 including adverse event rates (AEs), serious adverse event rates (SAEs), study discontinuation rates, electrocardiograms (ECGs), vital signs, and laboratory safety observations.
Secondary The secondary objectives of this study will evaluate the effects of CST-2032 when combined with CST-107 versus placebo on the following measures: 
1. Cognition2. Mood3. Attention Deficit4. Apathy5. Overall clinical improvement6. PK	The secondary endpoints will compare the effect of CST-2032 administered with CST-107 versus placebo on the following: 
• Cognitive tasks in the Cambridge Neuropsychological Test Automated Battery (CANTAB) and other cognitive measures:
○ Reaction Time (RT) – attention○ Verbal Recognition Memory (VRM) – episodic memory (verbal stimuli)○ Adaptive Tracking Task (ATT) – visuospatial with strong attentional demand○ Paired Associates Learning (PAL) – episodic memory (visual stimuli)

	
○ Delayed Verbal Recall – episodic memory (verbal stimuli)○ Stop Signal Task (SST) – response inhibition (impulsivity), an aspect of executive function○ Phonological verbal fluency (pVFT)○ Digit symbol substitution test (DSST)○ Color Trails Test (select sites only)● Facial expression recognition task (FERT).● Geriatric Depression Scale – 30 questions (GDS-30).● Conners Adult Attention Deficit Hyperactivity Disorder (ADHD) Rating Scale, short form, self-report (CAARS).● Starkstein Apathy scale short form (SAS-6).● Alzheimer's Disease Cooperative Study-Clinical Global Impression of Change (ADCS-CGIC).● Suicidal ideation using the Columbia Suicide Severity Rating Scale (C-SSRS).● Plasma pharmacokinetics (PK) parameters of CST-2032 and CST-107 (including C_{max}, t_{max}, AUC_t, $t_{1/2}$).
--	--

Exploratory

The exploratory objectives are:

- To evaluate whether baseline disease characteristics impact response to treatment.
- To characterize the effects of treatment on neurodegenerative biomarkers in the blood such as neurofilament light chain, total and phosphorylated tau protein, and amyloid- β (A β) peptides may also be measured.

The following exploratory endpoints may be undertaken to evaluate:

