6 DATA ANALYSIS CONSIDERATIONS

6.1 General Data Handling

All analyses will be conducted based on SAS 9.4 or higher.

Study data will be recorded in eCRFs for all screened and randomized patients. The EDC vendor for this study is MedNet Solutions.

Unless otherwise stated, all listings will be sorted by disease type, treatment sequence, subject number, and assessment date (and time, if available).

Unless stated otherwise, continuous data will be summarized by disease type, treatment sequence, and overall using n, mean, median, standard deviation (SD), minimum value, and maximum value.

Unless stated otherwise, categorical data will be summarized by disease type, treatment sequence, and overall using frequency counts and percentages. Where applicable, 95% confidence intervals (CIs) will be provided. Unless otherwise stated, the denominator of percentages will be the number of participants in the population/treatment arm or the number with non-missing data.

- The number of missing values will be presented as a separate category with no percentage, but only if one or more subjects are missing data.
- Counts of zero will be presented without percentages.

Relative to the number of digits after the decimal in the raw data, summary statistics will have the following number of digits after the decimal:

- Minimum and Maximum: same number of significant digits as the raw data
- Mean and Median: one additional decimal place to that reported for Minimum and Maximum
- SD or Standard Error (SE): two additional decimal places than the Minimum and Maximum
- Percentages: reported to one decimal place
- P-values will be reported to four decimal places. If the value is below 0.0001 it will be noted as < 0.0001; if the value is above 0.9999 it will be noted as > 0.9999.

Unless otherwise noted, statistical inference will be based on a 5% significance level (i.e. 95% confidence intervals will be produced).

All data up to the time of study completion/withdrawal from the study will be included in the analysis, regardless of duration of treatment.

Numbering for data displays will be based on ICH E3.

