9.1 Primary Endpoint and Analyses

The SAF will be used for all primary endpoint analyses unless otherwise stated otherwise. The primary objective of this study is to evaluate the safety and tolerability of CST-2032 when combined with CST-107. Further details regarding safety analyses can be found in Section 11.

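### Study discontinuation, a primary endpoint component, is tabulated by sequence and not by treatment, so the SAP yields no active-versus-placebo rate of all-cause dropout

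*SAP*

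**What the plan says.** - **Endpoint.** SAP 3 includes in the primary endpoint "study discontinuation rates, electrocardiograms (ECGs), vital signs, and laboratory safety observations". The Protocol synopsis and Protocol 2.2 name the same components.
- **Protocol, main text.** Protocol 8.7: "Primary endpoint data will be summarized by treatment using the Safety Set". Protocol 8.5 and 8.5.1 ask for disposition by treatment as well as by sequence, and 8.5.1 wants the number of subjects "entering the treatment period, completing each period, completing the study, and discontinuing study prematurely".
- **Protocol synopsis.** The Statistical Analysis entry gives disposition by disease criteria, sequence and overall, without treatment. The same entry asks for safety summaries by active versus placebo.
- **SAP 8.1.** In the ITT set it counts subjects "completing the study, and discontinuing study prematurely, including a description of the reason for early withdrawal", with eleven reason categories, and then states "Data will be presented by disease criteria and sequence". It has no line for entering or completing a period.
- **SAP 6.1.** The default is no help: "categorical data will be summarized by disease type, treatment sequence, and overall using frequency counts and percentages".
- **SAP 9.1.** It names the Safety Set for the primary endpoint and adds "Further details regarding safety analyses can be found in Section 11". Section 11 covers adverse events, laboratory results, vital signs, ECG, physical examination and the C-SSRS. It has no analysis of study discontinuation.
- **SAP 11.1.** It counts adverse events that led to withdrawal of treatment and attributes each event to the treatment of the period. Washout events go to the Period 1 treatment.
- **SAP 2.1.** The only change it declares concerns Type I error and the ordering of hypotheses.

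**The concern.** The trial is descriptive and plans no test of its primary endpoint, so for this component the tabulation is the analysis. A tolerability question needs the rate on active set against the rate on placebo. In a two-period crossover each sequence column holds one active and one placebo period, so the columns differ in order and not in exposure. Subjects who leave because they feel unwell but are recorded as withdrawn consent, study burden, investigator decision or lost to follow-up would appear only in a table that cannot place them on drug or placebo. The disposition table (14.1.1) is also among the outputs for the DSMB at the optional interim analysis. At that point some subjects may be in Period 1 and others in Period 2, which makes sequence columns harder still to read.

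**Working it through.** **Inputs.** Two sequences, active then placebo (AP) and placebo then active (PA), allocated 1:1 (SAP 4.2). About 60 subjects (SAP 4.3), so about 30 per sequence. The documents state no dropout rate, so there is no plan figure to reproduce. All risks below are assumptions: pA per active period, pP per placebo period.

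**Step 1: what the sequence table shows when risk depends on treatment alone.**

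- AP: pA + (1 - pA)pP = 1 - (1 - pA)(1 - pP)
- PA: pP + (1 - pP)pA = 1 - (1 - pP)(1 - pA)

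The two are identical for any pA and pP.

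| pA / pP | AP | PA | Expected dropouts per 30 |
|---|---|---|---|
| 10% / 5% | 14.5% | 14.5% | 4.35 |
| 20% / 5% | 24.0% | 24.0% | 7.2 |
| 30% / 5% | 33.5% | 33.5% | 10.05 |

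Variation in risk between subjects does not break the equality, because the expression is symmetric within each subject. Nor does a Period 2 factor k that multiplies the probability of staying in: retention is k(1 - pA)(1 - pP) in both sequences.

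**Step 2: relax those conditions**, with 20% / 5% as the Period 1 risks and a true Period 1 difference of +15 points.

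With a Period 2 odds ratio of 0.5, active odds go from 0.25 to 0.125 (11.1%) and placebo odds from 0.0526 to 0.0263 (2.56%). Then AP = 1 - 0.80 × 0.9744 = 22.1%, and PA = 1 - 0.95 × 0.8889 = 15.6%. The other rows follow in the same way. For carryover, placebo after active is given a 10% risk: AP = 1 - 0.80 × 0.90 = 28%.

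| Assumption | AP | PA | AP - PA |
|---|---|---|---|
| Period 2 odds ratio 0.25 | 21.0% | 10.6% | about +10.5 points |
| Period 2 odds ratio 0.5 | 22.1% | 15.6% | +6.5 points |
| Period 2 odds ratio 2 | 27.6% | 36.7% | about -9 points |
| Carryover, no period effect | 28% | 24% | +4 points |

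The same drug effect can therefore appear as nothing, as a smaller excess in AP, or as an excess in PA.

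**Step 3: the same data by treatment at discontinuation** (20% / 5%).

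- Dosed with active: 30 + 30 × 0.95 = 58.5. Dosed with placebo: 30 + 30 × 0.80 = 54.
- No period effect: 58.5 × 0.20 = 11.7, or 20%, against 54 × 0.05 = 2.7, or 5%.
- Odds ratio 0.5: active (6 + 28.5 × 0.1111)/58.5 = 15.7%; placebo (1.5 + 24 × 0.0256)/54 = 3.9%. Difference +11.8 points.
- Odds ratio 2: active (6 + 28.5 × 0.3333)/58.5 = 26.5%; placebo (1.5 + 24 × 0.0952)/54 = 7.0%. Difference +19.5 points.
- Carryover: active 20%; placebo (1.5 + 24 × 0.10)/54 = 7.2%. Difference +12.8 points.

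The by-treatment table keeps the direction in all four cases. Carryover still shrinks the difference, because late losses due to the drug are counted against placebo.

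**The case against.** Five arguments run the other way.

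1. **AE-driven withdrawal is already split by treatment.** SAP 11.1 attributes it to the treatment of the period, washout included, and SAP 8.7 summarizes exposure by treatment. This stands. A reader might infer that the SAP says nothing by treatment about tolerability dropout; it does for dropout recorded as an adverse event. What has no by-treatment table is all-cause dropout and the non-AE reasons.
2. **SAP 8.1 follows the Protocol synopsis.** This also stands. A reader might infer that the SAP silently overrode a settled protocol rule. The Protocol is in fact inconsistent with itself, and the SAP matches one of its statements. But Protocol 8.5, 8.5.1 and 8.7 all name treatment, and the synopsis wants safety data by active versus placebo.
3. **Protocol 8.7 remains in force.** The SAP is to be read with the Protocol, and Protocol 8.5 lets changes be documented in the SAP or the study report. So silence in SAP 2.1 is weak evidence of an undeclared change. It does not supply the missing table, attribution rule or denominator.
4. **The study is descriptive and small.** Treating person-periods as independent, the rough power for 10% against 5% is 17%, so a modest difference would stay unclear after the fix. Power is 67% for 20% against 5% and 94% for 30% against 5%, so a large one need not.
5. **The listings would allow the table to be built later.** True, but the attribution rule would then be chosen after unblinding.

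**Conclusion.** The point holds. For a named component of the primary endpoint, the SAP's only tabulation is by disease and sequence. That contrast does not estimate the drug's effect on discontinuation, and no other section gives all-cause or non-AE discontinuation by treatment.

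A reader might go further and infer that the two sequences must show the same expected rate whatever the drug does. The documents do not support that. Equality needs dropout risk to depend on treatment alone, or period to act as a multiplier on retention, and in either case no carryover. Nothing in the plan guarantees these conditions. Without them the sequence difference ranged from about -9 to +10.5 points in the assumed cases, against a true Period 1 difference of +15. The sound conclusion is that the contrast is uninterpretable as a drug effect, not that it is always zero.

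The percentages are illustrations on assumed risks. The structural defect does not depend on them. It should be corrected before database lock.

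**What to change.** - **SAP 8.1 and 9.1:** add a Safety Set table of study discontinuation, all-cause and by each reason, by treatment received at discontinuation. The denominator is the number of subjects dosed with that treatment. Assign losses during washout to the Period 1 treatment, as SAP 11.1 does for adverse events.
- **SAP 8.1:** restore the numbers entering and completing each period, and keep the by-sequence table as a secondary display.
- **Protocol:** reconcile the synopsis wording on disposition with Protocol 8.5, 8.5.1 and 8.7.

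The cost is some SAP wording, one extra table from data already collected, and a synopsis correction.

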8.2 Protocol Deviations

Protocol deviations will be recorded and detailed in a data listing. Protocol deviations will be identified and classified as minor or major, as evaluated by the monitoring team.

Protocol waiver data will also be recorded and detailed in a data listing.

8.3 Demographic and Baseline Characteristics

Subject demographics using the ITT set will be summarized. These will include age, sex (Male / Female), child-bearing potential (Yes / No), ethnicity (Hispanic or Latino / Not Hispanic or Latino), race (American Indian or Alaska Native / Asian / Black or African American / Native Hawaiian or Pacific Islander / White / Other), years of education, baseline height (cm), baseline weight (kg), and BMI (kg/m²). Data will be presented by disease criteria and sequence.

8.4 Clinical and Cognitive Scales

The Montreal Cognitive Assessment (MoCA) is a brief cognitive screening tool and includes measures of expressive and receptive language, memory, and praxis. There are items that screen executive functions and working memory. The scores range from 0 to 30 with scores lower than 26 suggesting cognitive disorder.

The Digital Symbol Substitution Test (DSST) integrates complex neuropsychological processes and measures aspects of cognitive function, including cognitive and psychomotor speed, attention, visual scanning, and executive function. The maximum attainable score is 135, with higher scores indicating better performance. Further details of the test can be found in Section 5.3.6.1 of the study protocol.

The Modified Hoehn and Yahr Scale (MHYS, for PD subjects only) is a clinician-completed rating scale that is used to describe the symptom progression of PD. It parses PD into 5 stages, with the additional of stages 1.5 and 2.5 to account for the intermediate course of PD. Details on staging can be found in Section 5.3.6.8 of the study protocol.

The REM Sleep Behavior Disorder Single-Question Screen (RBD1Q) is a single “yes-no” question as follows: “Have you ever been told, or suspected yourself, that you seem to ‘act out your dreams’ while asleep (for example, punching, flailing your arms in the air, making running movements, etc.)?” RBD1Q will be evaluated for all subjects but used to assess eligibility for only PD subjects.

MoCA, DSST, MHYS, and RBD1Q data will be summarized in the demographics and baseline characteristics tables and listed by subject.

8.5 Medical History

Medical history among the ITT set will be summarized and listed by Medical Dictionary for Regulatory Activities (MedDRA 24.1) system organ class (SOC) and preferred term (PT), and verbatim term as collected in the study database.

8.6 Prior, Concomitant, and Rescue Medication

The incidence of medication use will be summarized by WHO Drug Dictionary (B3 2021-09-01) anatomic therapeutic chemical (ATC) Level 2 classification (i.e. therapeutic main group) and preferred name. A subject will be counted only once at each level of reporting. Prior medications are those which have been identified to have been discontinued prior to the treatment start date (e.g. taken exclusively during the pre-therapy period and prior to the start of CST-2032 or matching placebo on Day 1). Concomitant medications are those which have been identified to have been taken at any point after first dose. Subjects who are administered rescue medications are those which have been administered rescue nadolol when there is an intolerable HR/BP increase. Prior, concomitant, and rescue medication use will be summarized separately and presented by disease and treatment group.

All prior, concomitant, and rescue medication data will be listed including the verbatim and preferred drug name and ATC Level 2. Procedures and non-medication therapies will also be listed.

8.7 Study Drug Exposure and Compliance

Drug exposure will be summarized as a continuous variable in the Safety Set. The duration of drug exposure will be calculated as follow:

$$\text{Duration of Exposure (days)} = \text{Date of Last Dose} - \text{Date of First Dose} + 1$$

In addition, subjects will be assessed for compliance to drug dosing for CST-2032 and CST-107 based on number of tablets dispensed and returned will be provided. The total number of tablets taken will be calculated as the sum of tablets dispensed minus the sum of tablets returned.

- 28 CST-2032 or placebo tablets are expected to be taken during each treatment period, per protocol (i.e., two tablets once daily beginning on Day 1). Summaries will be presented by treatment (i.e., Placebo and CST-2032/CST-107) based on each subject's exposure to each treatment.
- 15 CST-107 or placebo tablets are expected to be taken during each treatment period, per protocol (i.e., one tablet once daily beginning on Day -1). Summarized will be presented by treatment (i.e., Placebo and CST-2032/CST-107) based on each subject's exposure to each treatment.

Drug exposure will be summarized by disease type and treatment taken at time of data collection.

Study drug administration data, including date and time of doses, location of dosing, total number of tablets dispensed and returned, and compliance will be listed.

9 ENDPOINT ANALYSES

All inferential analyses are exploratory in nature given that this study was not powered based on any statistical assumptions. All efficacy data will be presented by cohort, disease type, and treatment assigned at the time of data collection.

9.1 Primary Endpoint and Analyses

The SAF will be used for all primary endpoint analyses unless otherwise stated otherwise. The primary objective of this study is to evaluate the safety and tolerability of CST-2032 when combined with CST-107. Further details regarding safety analyses can be found in Section 11.

9.2 Secondary Endpoints and Analyses

The FAS will be used for all secondary endpoint analyses unless stated otherwise. All inferential analyses are exploratory in nature given that this study was not powered based on any statistical assumptions.

CANTAB

Cognition function is assessed using the following CANTAB tests:

- Reaction Time (RTI)
- Verbal Recall Memory (VRM)
- Adaptive Tracking Task (ATT)
- Paired Associates Learning Task (PAL)
- Stop Signal Task (SST)
- Delayed Verbal Recall

The cognitive assessments measured as part of the CANTAB tests will be administered on Day - 1 (Baseline), and 3 hours after dosing on Days 1, 7, and 14 of each treatment period. Summaries will be presented by disease type and treatment sequence.

There are eighteen key measures based on the Measures Description downloaded from the CANTAB portal and as described by Cambridge Cognition, which are:

- RTI Median Five-Choice Movement Time: The median time taken for a subject to release the response button and select the target stimulus after it flashed yellow on screen, measured in milliseconds. The measurement name for this parameter in the files downloaded from the CANTAB portal is RTIFMDMT.
- RTI Median Five-Choice Reaction Time: The median duration it took for a subject to release the response button after the presentation of a target stimulus, measured in milliseconds. The measurement name for this parameter in the files downloaded from the CANTAB portal is RTIFMDRT.
- PAL First Attempt Memory Score: The number of times a subject chose the correct box on their first attempt when recalling the pattern locations. The measurement name for this parameter in the files downloaded from the CANTAB portal is PALFAMS.
- PAL Number of Patterns Reached: The number of patterns presented to the subject on the last problem they reached. The measurement name for this parameter in the files downloaded from the CANTAB portal is PALNPR.
- PAL Total Errors (Adjusted): The number of times the subject chose the incorrect box for a stimulus on assessment problems (PALTE), plus an adjustment for the estimated number of

errors they would have made on any problems, attempts and recalls they did not reach. The measurement name for this parameter in the files downloaded from the CANTAB portal is PALTEA.

- VRM Free Recall Distinct Stimuli – P1.1: The total number of distinct words that are correctly recalled from the presentation phase by the subject during the P1.1 immediate free recall stage. The measurement name for this parameter in the files downloaded from the CANTAB portal is VRMFR11D.
- VRM Free Recall Distinct Stimuli – P1.2: The total number of distinct words that are correctly recalled from the presentation phase by the subject during the P1.2 immediate free recall stage. The measurement name for this parameter in the files downloaded from the CANTAB portal is VRMFR12D.
- VRM Free Recall Distinct Stimuli – P1.3: The total number of distinct words that are correctly recalled from the presentation phase by the subject during the P1.3 immediate free recall stage. The measurement name for this parameter in the files downloaded from the CANTAB portal is VRMFR13D.
- VRM Delayed Free Recall Distinct Stimuli – P2.1: The total number of distinct words that are correctly recalled from the presentation phase by the subject during the P2.1 delayed free recall stage. The measurement name for this parameter in the files downloaded from the CANTAB portal is VRMFR21D.
- VRM Delayed Recognition Total Correct – P2.2: The total number of target words that the subject correctly recognizes, plus the total number of distractor words that the subject correctly rejects in the P2.2 delayed recognition phase. The measurement name for this parameter in the files downloaded from the CANTAB portal is VRMD22TC.
- VRM Free Recall Distinct Stimuli Mean – P1.1-1.3: The mean of times a subject repeats a word that was shown during the presentation phase in the P1.3 immediate free recall stage. The measurement name for this parameter in the files downloaded from the CANTAB portal is VRMFRDM.
- VRM Free Recall Distinct Stimuli Median – P1.1-1.3: The median number of distinct words that are correctly recalled from the presentation phase by the subject during the P1.1-1.3 immediate free recall stages. The measurement name for this parameter in the files downloaded from the CANTAB portal is VRMFRDMD.
- ATT Euclidean Distance Mean (Phase 2B): The mean Euclidean distance between Target x/y and Finger Touch x/y coordinates, calculated in pixel over the entire 2B assessed phase of the task. This measure is only calculated during the times that either 'Finger Lift' and/or 'Multi-touch' are not occurring. The measurement name for this parameter in the files downloaded from the CANTAB portal is ATT2BEM.
- ATT Euclidian Distance Standard Deviation (Phase 2B): The standard deviation of the Euclidean distance between Target x/y and Finger Touch x/y coordinates, calculated in pixels over the entire 2B assessed phase of the task. This measure is only calculated during the times that either 'Finger Lift' or 'Multi-touch' are not occurring. The measurement name for this parameter in the files downloaded from the CANTAB portal is ATT2BESD.
- ATT Difficulty Multiplier Mean (Phase 2B): The mean of the difficulty multiplier calculated over the entire 2B assessed phase of the task. This measure is only calculated during the times that either 'Finger/Lift' and/or 'Multi-touch' are not occurring. The measurement name for this parameter in the files downloaded from the CANTAB portal is ATT2BDM.

- ATT Difficulty Multiplier Standard Deviation (Phase 2B): The standard deviation of the difficulty multiplier calculated over the entire 2B assessed phase of the task. This measure is only calculated during the times that either 'Finger Lift' and/or 'Multi-touch' are not occurring. The measurement name for this parameter in the files downloaded from the CANTAB portal is ATT2BDSD.
- SST Stop Signal Reaction Time: The estimate of time where an individual can successfully inhibit their responses 50% of the time. This covert measurement is sampled from the length of time between the go stimulus and the stop stimulus at which the subject is able to successfully inhibit their response on 50% of the trials. We can infer that this is the time before which all actions become ballistic and the subject is no longer able to cancel their action selection. The measurement name for this parameter in the files downloaded from the CANTAB portal is SSTSSRT.
- SST Median RT: All Go Trials: The median reaction time taken across all the valid Go trials in the task. The measurement name for this parameter in the files downloaded from the CANTAB Portal is SSTMRTG.

Additionally, 3 more verbal recall parameters will be derived for analysis:

- VRM Free Recall Distinct Stimuli Mean Errors – P1.1-1.3: For each recording of VRMFRDM, a new record will be derived as the value of VRMFRDM subtracted from 18. The parameter decode will be VRMFRDME.
- VRM Delayed Free Recall Distinct Stimuli Errors – P2.1: For each recording of VRMFR21D, a new record will be derived as the value of VRMFR21D subtracted from 18. The parameter decode will be VRMFR21E.
- VRM Delayed Recognition Total Correct Errors – P2.2: For each recording of VRMD22TC, a new record will be derived as the value of VRMD22TC subtracted from 36. The parameter decode will be VRMD22TE.

For all 21 parameters, observed values at each assessment and changes from baseline will be summarized using descriptive statistics on the FAS and PPS. In addition to the descriptive statistic summaries, for each parameter, a mixed effects model approach will be used to evaluate treatment effect. The model will include change from baseline as the dependent variable, baseline as a covariate, treatment sequence, period, timepoint (i.e., Day 1: 3 hrs post-dose, Day 7: 3 hrs post-dose, Day 14: 3 hrs post-dose), disease type, and treatment as fixed effects, and subject as a random effect. The least square means will be summarized, as well as the least square mean difference between treatments, where the corresponding p-value for this LS mean difference will be provided. If there are convergence issues, alternative covariance structures may be used including autoregressive of order 1 (AR1) and compound symmetry (CS). The effect size will be estimated using Cohen's D: difference in means / pooled SD. This analysis will be performed using AD and PD as subgroups, and again using AD-MCI, AD-MD, PD-MCI, and PD-MD as subgroups.

Additionally, using treatment period 1 and treatment period 2 data separately, all 21 parameters will have observed value and change from baseline summarized, and a mixed effects model with change from baseline as the dependent variable, baseline as a covariate, timepoint (i.e., Day 1: 3 hrs post-dose, Day 7: 3 hrs post-dose, Day 14: 3 hrs post-dose), disease type, and treatment as fixed effects, and subject as a random effect will be evaluated. The least square means, least

square mean differences, and associated p-values will be presented. AR1 and CS covariance structures may be explored if there are convergence issues. The effect size will be estimated using Cohen's D: difference in means / pooled SD. These analyses will be presented by AD and PD subgroups and no further subgroup categorization. The analyses will be presented on the FAS and repeated on the PPS.

Bar plots of the arithmetic mean of observed values with error bars of the standard error of the mean, arithmetic mean of change from baseline with error bars of the standard error bars of the mean change, and least square mean change with error bars of the standard error will be produced for the following CANTAB parameters:

- VRM Free Recall Distinct Stimuli Mean – P1.1-1.3 (VRMFRDM)
- VRM Free Recall Distinct Stimuli – P1.1 (VRMFR11D)
- VRM Free Recall Distinct Stimuli – P1.2 (VRMFR12D)
- VRM Free Recall Distinct Stimuli – P1.3 (VRMFR13D)
- VRM Delayed Free Recall Distinct Stimuli – P2.1 (VRMFR21D)
- VRM Delayed Recognition Total Correct – P2.2 (VRMD22TC)

Bar plots of the least square mean change with error bars of the standard error only will be produced for the following CANTAB parameters:

- PAL Total Errors (Adjusted) (PALTEA)
- RTI Median Five-Choice Reaction Time (RTIFMDRT)
- RTI Median Five-Choice Movement Time (RTIFMDMT)
- ATT Difficulty Multiplier Mean (ATT2BDM)
- SST Stop Signal Reaction Time (SSTSSRT)

All plots will be presented separately for AD and PD subjects.

All CANTAB data, which includes 80 total measurements, will be listed on the FAS.

Phonological verbal fluency (pVFT)

The pVFTs are widely used for assessing executive function and requires the generation of words from initial letters (phonological verbal fluency) or belonging to a specific category (semantic fluency), under a time constraint. The specific versions of verbal fluency tests in this study are the 'ALPHABET' and 'CATEGORY' tests from the Brief And Simple Index of Cognition (BASIC).

For the ALPHABET task, subjects are given 1 minute to say aloud as many words they can think of that begin with the letter F, avoiding repetitions or the same words with different endings. The total score is the number of correct words generated. For the CATEGORY task, subjects are given 1 minute to say aloud as many animals they can think of, avoiding repetitions. The total score is the number of animals generated.

The pVFTs will be administered on Day -1 (Baseline), Day 1, Day 7, and Day 14 of each treatment period. Summary statistics of observed values and change from baseline will be

presented. A mixed model with change from baseline as the outcome, baseline as a covariate, fixed effects for treatment sequence, period, timepoint (i.e., Day 1, Day 7, Day 14), disease type, and treatment, and subject as a random effect will be analyzed. LS mean, LS mean difference and its associated p-value will be reported. AR1 and CS covariance structures may be explored if there are convergence issues. The effect size will be estimated using Cohen's D: difference in means / pooled SD. This analysis will be performed using AD and PD as subgroups, and again using AD-MCI, AD-MD, PD-MCI, and PD-MD as subgroups. The analysis will be presented on the FAS and repeated on the PPS.

Bar plots of the least square mean change of Alphabet and Category scores with error bars of the standard error will be produced, separated by AD and PD.

All pVFT data will be listed.

Facial Expression Recognition Task (FERT)

Analyses of FERT data will be summarized in a separate analysis plan.

Digital Symbol Substitution Test (DSST)

The DSST will be administered on Day -1 (Baseline), Day 1, Day 7, and Day 14 of each treatment period. Summary statistics of the total score observed values and change from baseline will be presented. A mixed model with change from baseline as the outcome, baseline as a covariate, fixed effects for treatment sequence, period, timepoint (i.e., Day 7, Day 14), disease type, and treatment, and subject as a random effect will be analyzed. LS mean, LS mean difference and its associated p-value will be reported. AR1 and CS covariance structures may be explored if there are convergence issues. The effect size will be estimated using Cohen's D: difference in means / pooled SD. This analysis will be performed using AD and PD as subgroups, and again using AD-MCI, AD-MD, PD-MCI, and PD-MD as subgroups. The analysis will be presented on the FAS and repeated on the PPS.

A bar plot of the least square mean change of DSST total score with error bars of the standard error will be produced, separated by AD and PD.

All DSST data will be listed.

Geriatric Depression Scale – 30 questions (GDS-30)

The GDS is a 30-item self-administered yes/no question test constructed for brief screening of depression in elderly persons. Total scores are the summation of scored responses (responses indicating worsening depression equate to 1, and responses indicating lessening depression equate to 0) from each question. Scores greater than 9 are considered suspect for depression. The GDS will be administered on Day -1 (Baseline), Day 1, and Day 14 of each treatment period. Summary statistics of total scores and change from baseline will be presented. A mixed model with change from baseline as the outcome, baseline as a covariate, fixed effects for treatment sequence, period, timepoint (i.e., Day 1, Day 14), disease type, and treatment, and subject as a random effect will be analyzed. LS mean, LS mean difference and its associated p-value will be

reported. AR1 and CS covariance structures may be explored if there are convergence issues. The effect size will be estimated using Cohen's D: difference in means / pooled SD.

All GDS data, included responses to individual questions, will be listed.

Conners Adult Attention Deficit Hyperactivity Disorder Scale (ADHD) Rating Scale, short form, self-report (CAARS)

The CAARS is a 26-item scale designed to assess, diagnose, and monitor treatment of attention deficit/hyperactivity disorder (ADHD) in adults. The self-report short form contains factor-derived scales for inattention/memory, hyperactivity/restlessness, impulsivity/emotional lability, and problems with self-concept. Individuals are asked to rate themselves on a range of symptoms and behaviors associated with ADHD as adults using a 4-point scale: 0=Not at all/never; 1=Just a little/once in a while; 2=Pretty much/often; 3=Very much/very frequently. The CAARS will be administered on Day -1 (Baseline), Day 1, and Day 14 of each treatment period. Total score will be derived as the sum of results from the 26 questions at each visit and can range from 0 to 78. Subscales will be derived as follows:

- Inattention/Memory Problems: sum of scores from questions 3, 5, 17, 18, and 21
- Hyperactivity/Restlessness: sum of scores from questions 4, 6, 10, 11, and 23
- Impulsivity/Emotional Lability: sum of scores from questions 1, 7, 8, 13, and 20
- Problems with Self-Concept: sum of scores from questions 9, 15, 16, 25, and 26
- ADHD Index: sum of scores from questions 2, 7, 8, 9, 11, 12, 14, 17, 19, 22, 24, and 26

Summary statistics of the 5 subscales and total scores and change from baseline will be presented. A mixed model with change from baseline as the outcome, baseline as a covariate, fixed effects for treatment sequence, period, timepoint (i.e., Day 1, Day 14), disease type, and treatment, and subject as a random effect will be analyzed. LS mean, LS mean difference and its associated p-value will be reported. AR1 and CS covariance structures may be explored if there are convergence issues. The effect size will be estimated using Cohen's D: difference in means / pooled SD.

All CAARS data, including responses to individual questions, will be listed.

Starkstein Apathy scale short form (SAS-6)

The SAS-6 is a 6-item questionnaire read by an examiner to measure the severity of apathetic symptoms. Each question has four possible answers: "not at all," "slightly," "some," or "a lot" which are scored on a 4-point Likert scale (range: 0–3). Total scores will be derived the summation of scored responses (higher scores indicate more severe apathy) from each question and can range from 0 to 18. The SAS-6 will be administered on Day -1 (Baseline), Day 1, and Day 14 of each treatment period. Summary statistics of total scores and change from baseline will be presented. A mixed model with change from baseline as the outcome, baseline as a covariate, fixed effects for treatment sequence, period, timepoint (i.e., Day 1, Day 14), disease type, and treatment, and subject as a random effect will be analyzed. LS mean, LS mean difference and its associated p-value will be reported. AR1 and CS covariance structures may be explored if there are convergence issues. The effect size will be estimated using Cohen's D: difference in means / pooled SD.

All SAS-6 data, included responses to individual questions, will be listed.

Alzheimer's Disease Cooperative Study-Clinical Global Impression of Change (ADCS-CGIC)

